1.3 Secondary Specific Aims

The single dose of intrapartum azithromycin prophylaxis (2 g) will be compared to placebo to accomplish the following secondary aims:

- Main Secondary Aim for Women at High-Risk for Infection Cohort:
 - a. To evaluate whether the risk of maternal death or sepsis differs among laboring women with and without high-risk for infection (high risk is defined as women with prolonged labor [≥ 18 hours] and/or prolonged membrane rupture [≥ 8 hours] at time of randomization).
- Other secondary specific Aims:
 - b. To evaluate the effectiveness in reducing the risk of individual components of the primary composite endpoints (i.e., maternal death, maternal sepsis, intrapartum/neonatal death, neonatal sepsis including specifically all-cause neonatal deaths and neonatal deaths due to sepsis).
 - c. To evaluate the effectiveness on the risk of intrapartum/neonatal death or sepsis in infants of laboring women at high-risk for infection because of prolonged labor (≥ 18 hours) and/or prolonged membrane rupture (≥ 8 hours).
 - d. To evaluate the effectiveness on the risk of maternal infections including clinical chorioamnionitis, endometritis, wound infections (perineal or Cesarean), abdominal or pelvic abscess, mastitis/breast abscess or infection, pyelonephritis, pneumonia and other bacterial infections in all laboring women as well as in those at high-risk for infection.
 - e. To evaluate the effectiveness in reducing the use of subsequent maternal antibiotic therapy from randomization to 42 days postpartum for any reason in all laboring women as well as in those at high-risk for infection.
 - f. To compare the use of health care resources. Use of health care resources will be measured in terms of maternal and neonatal duration of hospital stay, unscheduled visits, readmission, and admission to special care units/intensive care units in all laboring women and newborns as well as in those at high-risk for infection.
 - g. To assess maternal GI symptoms (e.g., nausea, vomiting, and diarrhea) and other reported side effects, as well as infant pyloric stenosis and type of culture positive infections

(antimicrobial resistance and maternal and infant microbiome diversity are compared in an ancillary study).

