2.2.2 Exclusion Criteria

- Non-emancipated minors (as per local regulations)
- Evidence of chorioamnionitis or other infection requiring antibiotic therapy at time of eligibility (however, women given single prophylactic antibiotics with no plans to continue after delivery should not be excluded).
- Arrhythmia or known history of cardiomyopathy.
- Allergy to azithromycin or other macrolides that is self-reported or documented in the medical record.
- Any use of azithromycin, erythromycin, or other macrolide in the 3 days or less prior to randomization.
- Plan for cesarean delivery prior to randomization.
- Preterm labor undergoing management with no immediate plan to proceed to delivery.
- Advanced stage of labor (>6 cm or 10 cm cervical dilation per local standards) and pushing **or** too distressed to understand, confirm, or give informed consent **regardless** of cervical dilation.
- Are not capable of giving consent due to other health problems such as obstetric emergencies (for example, antepartum haemorrhage) or mental disorder.
- Any other medical conditions that may be considered a contraindication per the judgment of the site investigator.
- Previous randomization in the trial.

Sites may choose to obtain written consent during antenatal care from pregnant women of the age of consent who plan to deliver vaginally in a facility and have no known medical exclusions. In this case, study staff must fully assess and confirm eligibility at the time of randomization. It may also be necessary to verbally re-confirm consent at the time of randomization, if required by local regulations. If it is determined that the study needs to be extended to accrue the planned sample size for HR cohort, then women who deliver prior to meeting HR criteria for randomization will be excluded.

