4.1 Data Forms

The following forms will be used for this study:

Form Name	Purpose	Key Data Elements	Data Source
Contact and Scheduling Form	To facilitate participant follow-up by documenting contact information and projected study visit schedule	Contact information, date of enrollment, date of follow-up visits	Participant interview, study calendar
Screening and Enrollment Form	To determine eligibility and record consent status	Screening date, review and confirmation of inclusion/exclusion criteria, consent status/date.	Participant interview/report, clinical assessment, provider report, medical records
Randomization Form	To confirm eligibility and track randomization	Eligibility confirmation, randomization date/time, drug administration date/time, any problems with drug administration (e.g., vomiting, dropped med, etc).	Study records, participant interview and observation

Form Name	Purpose	Key Data Elements	Data Source
Maternal Baseline Data Form	To collect additional maternal information	
 Demographic and baseline clinical data: admission date/time, EDD, GA, age, height, weight, pregnancy and medical history, etc. Events during labor and delivery: timing of onset of labor, prolonged labor, premature rupture of membranes, date/time/type of membrane rupture, date/time/type of delivery, indication for induction (if applicable), vital signs during labor (temp, HR, RR, BP), complications, etc. Events after delivery: complications, vital signs, etc. Infection assessment pre- and post-delivery Antibiotic treatment pre- and post-delivery Discharge information 	Participant interview/report, provider report, medical records
Neonatal Baseline Data Form	To collect information about the infant directly after delivery.	
 Sex Birthweight Delivery outcome (live or stillbirth) Complications Infection assessment Discharge information: date/time, status (discharged, transferred, died) 	Participant interview/report, provider report, medical records
Maternal and Neonatal Follow-up Form	To collect maternal and infant health status during follow-up visits at 3 days, 7 days and 42 days after delivery.	
 Timing follow-up Maternal and infant status since discharge: general status, symptoms, indication of infection, clinic visits, hospitalizations, antibiotic use Temperature 	In-person participant interview/report and clinical exam

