- h. To determine whether the effect on each of the primary outcomes differs by region (Africa, Latin America or Asia), any other antibiotic use during labor, and mode of delivery (cesarean or vaginal). Note that antibiotic use will not include use to treat any infections diagnosed after randomization as those will be outcomes.

These secondary aims will be assessed using the following outcomes.

- The individual components of the primary outcomes (i.e., maternal death, maternal sepsis, maternal death due to sepsis, intrapartum/neonatal death, neonatal sepsis including specifically all-cause neonatal deaths and neonatal deaths due to sepsis)

- Other Maternal Outcomes
 - Chorioamnionitis: Fever ($>100.4^{\circ}\text{F}/38^{\circ}\text{C}$) in addition to one or more of the following: fetal tachycardia ≥ 160 bpm, maternal tachycardia > 100 bpm, tender uterus between contractions, or purulent/foul discharge from uterus **prior** to delivery.
 - Endometritis: Fever ($>100.4^{\circ}\text{F}/38^{\circ}\text{C}$) in addition to one or more of maternal tachycardia > 100 bpm, tender uterine fundus, or purulent/foul discharge from uterus **after** delivery.
 - Wound infection refers to purulent infection (superficial or deep infection including necrotizing fasciitis) of a perineal wound or wound of a cesarean with or without fever; In the absence of purulence, a wound infection requires presence of fever ($>100.4^{\circ}\text{F}/38^{\circ}\text{C}$) and at least one of the following signs of local infection: pain or tenderness, swelling, heat, or redness around the incision/laceration.
 - Other infections:
 - Abdominopelvic abscess is evidence of pus in the abdomen or pelvis noted during open surgery, interventional aspiration or imaging;
 - Mastitis/breast abscess or infection refers to fever ($>100.4^{\circ}\text{F}/38^{\circ}\text{C}$) and one or more of the following: breast pain, swelling, warmth, redness, or purulent drainage (for breast abscess).
 - Pyelonephritis refers to fever ($>100.4^{\circ}\text{F}/38^{\circ}\text{C}$) and one or more of the following: urinalysis/dip suggestive of infection or costovertebral angle tenderness or confirmatory urine culture.
 - Pneumonia refers to fever ($>100.4^{\circ}\text{F}/38^{\circ}\text{C}$) and clinical symptoms suggestive of lung infection including cough and/or tachypnea or radiological confirmation.
 - Use of subsequent maternal antibiotic therapy after randomization to 42 days postpartum for any reason.

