Maternal Other Infections	Binary	
The event will be defined as “Yes” if the criteria for any of the following infections are met prior to day 42 and “No” otherwise. Indicators will be also defined separately for each infection type.
 
 • Abdominopelvic abscess • Mastitis/breast abscess or infection • Pyelonephritis • Pneumonia • Other bacterial infection 
The details of defining this outcome are in the adjudication plan. In brief, where possible the outcome will be defined programmatically per the algorithm defined in the adjudication plan with cases that are unable to be programmatically determined route to adjudication. For the adjudicated outcomes, the value will be determined based on the reported final outcome reported by the site via form AZ13 (and confirmed via central adjudication). For each type, if the final outcome is “Insufficient data to make a determination,” the outcome will be treated as missing. For the overall, if no criteria were met for any of the infections and at least one is “Insufficient data to make a determination,” then composite outcome will be treated as missing.
 
Analysis population(s): ITT (all-comer and high risk)

Maternal antibiotic therapy after randomization to 42 days for any reason	Binary	
The outcome will be defined as “Yes” if any antibiotic therapy is reported on AZ03 during initial hospitalization, or on AZ05a, AZ06 or AZ07 during follow-up and prior to day 42 and “No” otherwise. The outcome will only be missing for mothers that are lost to follow-up prior to completion of a Day 7 visit and had no antibiotic use reported prior to becoming LTF.
 
Analysis population(s): ITT (all-comer and high risk)

Variable	Type	Definition
Time from drug administration until initial discharge after delivery (days)	Continuous	
Defined as the date/time of initial discharge reported on AZ03 or AZ07 – date/time of study drug administration reported on AZ02
 
Analysis population(s): ITT (all-comer and high risk)

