Maternal GI symptoms including nausea, vomiting, and diarrhea and other reported side effects.	Binary	
The outcome will be defined as “Yes” if vomiting or diarrhea are reported after delivery on AZ03 or AZ05a; an unscheduled care visit for nausea, vomiting, or diarrhea is reported on AZ05a; or an unscheduled care visit for nausea, vomiting and/or diarrhea is reported on AZ07; or a mechanistically-related AE is reported (e.g. abdominal pain); and “No” otherwise. The outcome will only be missing for mothers that are lost to follow-up prior to completion of a Day 7 visit and had no symptoms or side effects reported prior to becoming LTF.
 
Analysis population(s): As Treated

Neonatal Other Infections	Binary	
The event will be defined as “Yes” if any infection is reported that does not qualify for sepsis prior to day 28 and “No” otherwise. Other neonatal infections include eye infection with swelling and drainage, skin infection with 10 or more pustules or bullae, omphalitis, urinary tract infection, pyelonephritis or kidney infection, pneumonia or lung infection, meningitis, other infection documented in clinical record or respiratory rate ≥ 60. The outcome will only be missing for infants that are lost to follow-up prior to completion of a Day 7 visit and neonatal deaths prior to 7 days that do not qualify for sepsis or other infections.
 
Analysis population(s): ITT (all-comer and high risk)

Variable	Type	Definition
Neonatal initial hospital length of stay	Ordinal	Defined as the date/time of initial discharge reported on AZ04 or AZ08 – date/time of delivery reported on AZ03 Analysis population(s): ITT (all-comer and high risk)
Neonatal readmissions within 42 days of delivery	Binary	Only defined for live births who were initially discharged from the hospital following delivery as documented on AZ04 or AZ08 (i.e. stillbirths or infants that die during the initial hospitalization for delivery will be excluded from the numerator and denominator). The outcome will be defined as “Yes” if the location of any subsequent study visit on AZ05b is In-patient (hospitalized), or if there is an AZ08 form where the infant is noted as admitted or has a non-missing admission date; and “No” otherwise. The outcome will only be missing for infants that are lost to follow-up prior to completion of a Day 7 visit and had no readmission reported prior to becoming LTF. Analysis population(s): ITT (all-comer and high risk)

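### The SAP 9.2 rule for subsequent maternal antibiotic use omits the randomization start given in its own title, so earlier antibiotics could be counted and would pull the relative risk toward 1

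*Combined protocol and SAP*

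**What the plan says.** Three places start this outcome at randomization. The aim in protocol 1.3(e) concerns "reducing the use of subsequent maternal antibiotic therapy from randomization to 42 days postpartum for any reason". SAP 3.2 lists the outcome as "Use of subsequent maternal antibiotic therapy after randomization to 42 days postpartum for any reason". The row in SAP 9.2 is titled "Maternal antibiotic therapy after randomization to 42 days for any reason".

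The derivation rule in that row scores Yes if "any antibiotic therapy is reported on AZ03 during initial hospitalization", or if antibiotics appear on one of three follow-up forms before day 42. It gives an end to the window but no beginning.

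Three other provisions bear on this:

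- Protocol 2.2.2 says that "women given single prophylactic antibiotics with no plans to continue after delivery should not be excluded".
- Protocol 4.1 lists among the contents of the Maternal Baseline Data Form "Antibiotic treatment pre- and post-delivery", a split at delivery rather than at randomization.
- Protocol 4.1 also shows that the Randomization Form captures the date and time of randomization.

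**The concern.** An antibiotic given before randomization cannot be changed by the study drug. Counting it as an event adds the same expected number of events to each arm and shrinks the relative contrast.

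Reduced later antibiotic use is a named secondary aim. It is also part of the protocol's answer to the worry about resistance (protocol 1.6.3, point c). SAP 9.5 says that the secondary models are there to estimate relative risks rather than to test hypotheses, so a shift in the estimate is a shift in the very thing to be reported.

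**Working it through.** **Could a pre-randomization antibiotic reach this variable?**

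1. *Form.* The documents never pair the code AZ03 with a form name. SAP 9.2 takes the "date/time of delivery reported on AZ03" and also takes the initial discharge time from it. That matches the Maternal Baseline Data Form, which holds antibiotic data from before and after delivery. The link is an inference, though a strong one.
2. *Time in hospital before randomization.* Protocol section 2 has screening begin at admission and continue through the stay, so such time exists.
3. *Eligibility.* Single-dose prophylaxis is allowed under protocol 2.2.2.
4. *A start limit elsewhere.* The only general post-randomization restriction, in SAP 3.1, concerns infections. Other SAP 9.2 rows put the limit in the rule itself: the gastrointestinal-symptom row takes vomiting and diarrhea from AZ03 only after delivery, and the maternal unscheduled-visit row counts only care after the initial discharge. The antibiotic row has no such limit.

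Read literally, the rule therefore admits these antibiotics.

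**Direction and size.** The documents give no rate, effect size or power for this outcome, so there is no planned figure to reproduce. All rates below are assumptions.

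- q: share of women in each arm with an in-hospital antibiotic before randomization, equal in expectation because allocation is random
- p0: placebo rate of antibiotic use after randomization
- RR: true relative risk for use after randomization
- earlier and later use independent

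Observed RR = [q + (1 − q)·p0·RR] / [q + (1 − q)·p0]

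Equivalently, observed RR − 1 = (1 − q)·p0·(RR − 1) / [q + (1 − q)·p0]. For q > 0 and RR other than 1 this keeps its sign and shrinks, so the bias is toward 1.

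The two extremes for a true RR of 0.80:

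- q = 2%, p0 = 40%: (0.02 + 0.98 × 0.32) / (0.02 + 0.98 × 0.40) = 0.3336 / 0.4120 = 0.810
- q = 20%, p0 = 10%: (0.20 + 0.80 × 0.08) / (0.20 + 0.80 × 0.10) = 0.264 / 0.280 = 0.943

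Observed RR over the grid:

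| True RR | p0 | q = 2% | q = 5% | q = 10% | q = 20% |
|---|---|---|---|---|---|
| 0.80 | 10% | 0.834 | 0.869 | 0.905 | 0.943 |
| 0.80 | 20% | 0.819 | 0.842 | 0.871 | 0.911 |
| 0.80 | 40% | 0.810 | 0.823 | 0.843 | 0.877 |
| 0.70 | 10% | 0.751 | 0.803 | 0.858 | 0.914 |

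With q = 0, the observed and true values agree.

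**The case against.** A reader might infer that the trial does count pre-randomization antibiotics as outcomes. The documents do not support that, for these reasons:

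- **The title supplies the window.** The row title, SAP 3.2 and the protocol aim all begin at randomization. A programmer could take the window from the title and only the source forms from the sentence below it. This stands, so the text supports could be counted, not are counted. It does not make the rule sound, because the SAP writes start limits into other rules.
- **Therapy may not mean prophylaxis.** The protocol abstract and section 2.2.2 separate antibiotic therapy for infection from prophylaxis, and women needing therapy at eligibility are excluded. If the rule uses the word in that narrow sense, few pre-randomization antibiotics remain to be counted. The words about any reason in the title point the other way. The question is open.
- **The form is not visible.** Pre-delivery entries include the interval from randomization to delivery, and nothing shows whether AZ03 holds start times. Aim 1.3(h) separates other antibiotics in labor from treatment of infections diagnosed after randomization, which suggests that reason or timing is recorded somewhere.
- **The size is assumed.** Dilution is greatest when later use is low. If any antibiotic for any reason counts, later use includes prophylaxis given after randomization and may well exceed 10%. That is why the table varies p0. Positive association between earlier and later use would reduce the dilution further.

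The change summary for SAP version 2.0 notes only that forms were added to this row. Its silence on timing is not evidence that the window in the title was abandoned.

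**Conclusion.** The rule and its title do not agree. Followed literally, the rule would admit events that treatment cannot affect, and the relative risk would be biased toward 1. For a true relative risk of 0.80 the reported value would be about 0.81 to 0.94. This assumes pre-randomization use of 2% to 20%, equal across arms, later placebo use of 10% to 40%, and independence of the two. None of these rates comes from the documents. There is no bias if no woman had an antibiotic recorded before randomization, or if the programming applies the window in the title.

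The consequence is limited. SAP 7.5 classes this outcome as exploratory, with descriptive p-values and intervals. The primary tests, the sample size and the interim rule are untouched. This is a minor point, worth correcting because the correction is cheap.

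**What to change.** In the AZ03 clause of SAP 9.2, count only antibiotics started after the randomization date and time on the Randomization Form, and report earlier antibiotics as a baseline characteristic. State in the same row:

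- whether prophylaxis counts
- how undated entries are classified
- how courses begun before randomization and continued after it are classified

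If AZ03 records antibiotic timing, the cost is a few lines of text and one date-time comparison in the programming. If it does not, the SAP should say so and add a sensitivity analysis restricted to the post-delivery entries on AZ03 plus the follow-up forms. The downside of that analysis is that it omits antibiotic use between randomization and delivery, so it should accompany the main estimate rather than replace it.

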3.1.3 Secondary Analyses – Other Secondary Outcomes

Other maternal and neonatal binary outcomes including: the individual components of the primary outcomes, neonatal deaths due to sepsis, maternal infections (clinical chorioamnionitis, endometritis, wound infections (perineal or subsequent cesarean), pyelonephritis and pneumonia), use of subsequent maternal antibiotic therapy, pyloric stenosis and occurrences of maternal or neonatal readmission or admission into special care unit will be analyzed using the approaches detailed in **Section 3.1.1** for the ITT population and approaches detailed in **Section 3.1.2** for the HR cohort. A similar process with generalized linear models employing an appropriate link function will be used to analyze the outcomes of maternal and neonatal initial hospital length of stay.

Binary safety outcomes, e.g., nausea, vomiting, and diarrhea, will also be analyzed using the approaches detailed in **Section 3.1.1**. These analyses will be conducted using the As Treated population.

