 - Time from drug administration until initial discharge after delivery (time may vary by site).
 - Maternal readmission within 42 days of delivery.
 - Maternal admission to special care units.
 - Maternal unscheduled visit for care.
 - Maternal GI symptoms including nausea, vomiting, and diarrhea and other reported side effects.
 - Maternal death due to sepsis using the Global Network algorithm of causes of death.
- Other Neonatal Outcomes
 - Other neonatal infections (e.g. eye infection, skin infection, omphalitis, urinary tract infection, respiratory rate ≥ 60 breaths/minute)

- Neonatal initial hospital length of stay, defined as time of delivery until initial discharge (time may vary by site).
- Neonatal readmission within 42 days of delivery.
- Neonatal admission to special care units.
- Neonatal unscheduled visit for care.
- Neonatal death due to sepsis using the Global Network algorithm for causes of death.
- Pyloric stenosis within 42 days of delivery, defined as clinical suspicion based on severe vomiting leading to death, surgical intervention (pyloromyotomy) as verified from medical records, or radiological confirmation.

Detailed definitions for deriving the associated variables are included in Section 9.

Type of culture positive infections, antimicrobial resistance and maternal and infant microbiome diversity were compared in an ancillary study and the associated analyses described in a separate analysis plan.

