9.2 Definition of Analysis Variables

As clinical assessments/diagnoses and associated care may lag behind actual occurrence, any infection events, antibiotic use, or other medical care (e.g. admissions, unscheduled visits) documented prior to the end of the relevant visit window will be counted. Mortality outcomes will be defined in accordance with traditional Global Network algorithms only including events occurring specifically within the window detailed in the outcome definition below.

Additionally, most infections are expected to occur within the first week following delivery. Therefore, mothers or infants that are lost to follow-up after completion of a Day 7 visit with no signs or symptoms of infection prior to becoming lost to follow-up will be considered to meet criteria to have the primary outcome ascertained as no infection or death. Mothers or infants lost to follow-up prior to completion of a Day 7 visit with no signs or symptoms of infection will be considered to have missing outcomes.

Variable	Type	Definition
Primary Outcomes		
Maternal death and/or sepsis through 42 days Primary Composite Outcome	Binary	
The event will be defined as “Yes” if either component of this composite outcome is “Yes” and “No” if both components of the composite are “No.” Any subsequent missing values will be included in the primary analyses using multiple imputation procedures.
 
Analysis population(s): ITT (all-comer and high risk; with and without imputation), Per-Protocol

Intrapartum/neonatal death and/or sepsis through 28 days Primary Composite Outcome	Binary	
The event will be defined as “Yes” if either component of this composite outcome is “Yes” and “No” if both components of the composite are “No.” Any subsequent missing values will be included in the primary analyses using multiple imputation procedures.
 
Analysis population(s): ITT (all-comer and high risk; with and without imputation), Per-Protocol

Secondary Outcomes		
Maternal death through 42 days Component	Binary	
The event will be defined as “Yes” if the woman dies prior to 42 days after delivery and “No” otherwise. This outcome measure will be obtained from form MN06 (i.e. presence of a form indicating a death has occurred). If the 42-day outcome is missing and the woman was alive at the last known follow-up, this outcome will be treated as missing when analyzed alone.
 
Analysis population(s): ITT (all-comer and high risk), As Treated

Variable	Type	Definition

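### The maternal GI outcome in SAP 9.2 is narrower than its title: nausea has no direct-report route and vomiting recorded at dosing is not a source

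*Combined protocol and SAP*

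**What the plan says.** SAP 3.2 and Protocol 2.6 item i both name the outcome "Maternal GI symptoms including nausea, vomiting, and diarrhea and other reported side effects", and the row in SAP 9.2 carries the same title. None of these labels requires a visit or excludes the period before delivery. Protocol 3.1.3 adds: "Binary safety outcomes, e.g., nausea, vomiting, and diarrhea, will also be analyzed using the approaches detailed in" Section 3.1.1, in the As Treated population.

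The derivation in SAP 9.2 gives three routes to Yes:

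- Direct report: "if vomiting or diarrhea are reported after delivery on AZ03 or AZ05a".
- An unscheduled care visit for nausea, vomiting or diarrhea, recorded on AZ05a or AZ07.
- An adverse event judged mechanistically related, with abdominal pain as the example. No term list or time window is given.

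Everything else is No. The outcome is missing only for women lost before completing the Day 7 visit with nothing reported. SAP 9.5 assigns the outcome a relative risk and confidence interval. SAP 7.5 makes secondary p-values and intervals descriptive.

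**The concern.** The drug is taken once, in labor, directly after randomization (Protocol 2.3). Acute GI intolerance can therefore begin before the baby is born. Protocol 2.8 places side-effect surveillance in labor as well as postpartum, and Appendix 3 marks drug side effects in the column before delivery. Yet the only direct-report route in the derivation omits nausea and is tied to the time after delivery. It also bypasses the form on which vomiting at the dose would be noted.

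What is at stake is the meaning of one published tolerability figure. From the title, a reader would take it as the rate of nausea, vomiting and diarrhea following the dose. The rule counts something smaller. Because *after delivery* is not explained, two programmers could also code the same woman differently.

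**Working it through.** No figure in the plan needs reproducing, so the check is to apply the rule to typical cases and compare the results with the title.

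**Inputs.** The three routes and the missing-data rule are from SAP 9.2. Timing of the dose is from Protocol 2.3. Vomiting as an example of a problem with drug administration is from the Randomization Form entry in Protocol 4.1. The 15-minute vomiting exclusion is from the per-protocol definition in SAP 5.

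**Coding under each reading of *after delivery*.** Each woman is followed past Day 7, and no related adverse event is reported.

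| Case | Read as onset | Read as time of report |
|---|---|---|
| Nausea only, at any time, no unscheduled visit | No | No |
| Vomiting at the dose, on the Randomization Form only | No | No |
| Vomiting or diarrhea between dose and delivery, written on AZ03 after the birth | No | Yes |
| Vomiting or diarrhea starting after delivery, on AZ03 or AZ05a | Yes | Yes |
| Nausea leading to an unscheduled visit on AZ05a or AZ07 | Yes | Yes |

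1. The first two rows do not depend on the reading. Both women have a symptom named in the title, and both are coded No rather than missing.
2. The third row changes with the reading, and the SAP does not say which applies.
3. The second row conflicts in substance with SAP 5. Vomiting within 15 minutes of the dose removes a woman from the per-protocol set. The same woman stays in the As Treated population, where this outcome is analyzed, and can be counted there as having no GI symptom.
4. The adverse-event route could rescue some of these women. How many is unknown: the only adverse-event form listed in Protocol 4.1 is for serious or unexpected events, and the SAP lists no terms for this route.

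**Are the timing data available?** SAP 9.2 already uses the "date/time of study drug administration reported on AZ02" and the "date/time of delivery reported on AZ03". A symptom with its own recorded date and time could therefore be placed before or after delivery. Protocol 4.1 puts the time of the dose on the Randomization Form, so I take AZ02 to be that form. The documents show no labor-period field for nausea or diarrhea.

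**The case against.** The strongest reply is that the broader texts are labels. SAP 3.2 ends by sending the reader to Section 9 for detailed definitions, Protocol 2.6 item i is a single line, and Protocol 3.1.3 lists the symptoms only as examples. A derivation is often narrower than its label and may simply match what the forms collected. This stands in part: there are not two competing definitions. It does not answer the point that the row's own title promises nausea, or that vomiting captured at dosing is left unused.

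A second reply is that the information appears elsewhere. SAP 10 summarizes side effects with descriptive site-stratified p-values, and SAP 8.2 summarizes vomiting shortly after delivery, which may mean delivery of the drug. Both soften the loss. Neither enters the relative risk in SAP 9.5, and SAP 10 gives no derivation or window.

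The reply is right about three inferences that a reader might draw:

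- *That the SAP means onset.* The antibiotic row uses AZ03 with different words ("if any antibiotic therapy is reported on AZ03 during initial hospitalization"), but that wording follows its own window from randomization. The general rule that care "documented prior to the end of the relevant visit window will be counted" concerns late documentation, not when a window opens. Neither settles the reading.
- *That the loss can be counted.* One could multiply the protocol's single-dose rates (nausea 5-18%, vomiting 2-7%) by the arm size. Those rates are not stated to be for laboring women, no placebo rate is given, and neither symptom overlap nor the share caught by the visit and adverse-event routes is known. The product would not be a number of missed events.
- *That all labor symptoms were recorded and discarded.* Only vomiting is shown, and only as an example of an administration problem.

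**Conclusion.** The point holds as a mismatch between a stated counting rule and the outcome it is reported under. On either reading of *after delivery*, nausea without a visit or adverse-event report is coded No. So is vomiting recorded only on the Randomization Form. On the onset reading, directly reported vomiting or diarrhea confined to the time between dose and delivery is lost as well.

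The size is unknown. A reader might infer that the rule hides harm from azithromycin or biases the relative risk toward 1. The documents do not support that: vomiting in labor may occur in both arms, and leaving it out could move the estimate either way. The consequence is limited to a secondary safety outcome with descriptive inference; no primary or high-risk conclusion changes.

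The conclusion assumes that the SAP 9.2 row is the full derivation and that no adverse-event procedure outside these documents captures ordinary nausea or dosing vomiting.

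**What to change.** 1. State in SAP 9.2 whether *after delivery* means onset of the symptom or time of the report.
2. Add vomiting recorded on the Randomization Form and any labor-period GI items already collected. Show them separately from post-delivery events, so that labor-related vomiting does not dilute the existing post-delivery estimate.
3. Report nausea, vomiting and diarrhea separately where collected. This fits Protocol 3.1.3, and the SAP already does the equivalent for other maternal infections: "Indicators will be also defined separately for each infection type".
4. Where nausea or labor-period diarrhea was not collected directly, retitle the outcome to match what is counted and note the narrowing in SAP 12.

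As a side clarification, SAP 8.2 should say whether its vomiting summary runs from the birth or from taking the drug.

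The cost is SAP wording and a little extra derivation code, with no new data collection. For nausea and labor-period diarrhea the change may be only a retitle. The one statistical drawback is that labor vomiting in both arms may pull a combined relative risk toward 1; the separate display in item 2 keeps that visible.
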